3.4.2.3 Secondary Efficacy Analyses

IGA Score 0 or 1 with ≥ 2 Grade Reduction from Baseline to Week 16

The percentage of subjects achieving an IGA score of 0 (clear) or 1 (almost clear) and a reduction from baseline of ≥ 2 points at Week 16 will be analyzed using a logistic regression model including treatment group, randomization stratum (total serum IgE level < 150 kU/L or ≥ 150 kU/L), and baseline IGA as categorical factors. The coefficient of the treatment effects at Week 16 obtained from the logistic regression will then be used in an MCP-Mod analysis with 4 candidate models for the dose response (linear, E_{\max} , and 2 Hill- E_{\max} models). Details of the candidate models are provided in [Appendix 1](#). As part of the MCP-Mod model, the testing of the 4 candidate dose response models will be adjusted for multiplicity using a family-wise error rate of 0.10. If more than 1 candidate model shows a statistically significant dose response, the final model will be selected based on the Akaike Information Criteria obtained from each model.

The composite estimand of primary interest is the difference in IGA response rate at Week 16 between MEDI3506 and placebo in the ITT population. Subjects who withdraw from the study or require rescue therapy will be considered as non-responders. From the final model obtained

from the MCP-Mod dose response analysis, the difference in IGA response rate between the placebo and each MEDI3506 group will be estimated along with the 90% CI. For each MEDI3506 group versus placebo, the results will be presented as the difference in response rates, the 90% CI for the difference in response rates, and two-sided p-value.

A plot showing the percentage of subjects achieving IGA response in each treatment group by visit will be provided. In addition, barplot of IGA response rate at Week 16 in each treatment group will be provided.

Supplementary analyses will be performed to assess the sensitivity of the assumptions of the statistical methods used in the primary analysis for the IGA endpoint.

A logistic regression model of IGA response rate at Week 16 will be performed based on the ITT population. The model will include treatment group and randomization stratum (total serum IgE level < 150 kU/L or ≥ 150 kU/L) as categorical factors, and baseline IGA score as a covariate. Subjects who discontinue investigational product, withdraw from the study, or require rescue therapy will be considered as non-responders. For each MEDI3506 group compared with placebo, differences in response rates, 90% CIs for the differences in response rates (Ge et al, 2011), and two-sided p-values will be reported. If the number of responders is < 5 in any MEDI3506 group, the logistic regression model will not be used. Instead, the 90% CI and p-value for the difference in response rates will be calculated using an unconditional exact method (Chan and Zhang, 1999).

An analysis based on the ITT population will be done using all available data from subjects irrespective of whether or not they completed treatment, including data from subjects who received rescue therapy. Subjects who discontinue investigational product or withdraw from the study before Week 16 will be considered as non-responders. The analysis will be performed using the same MCP-Mod as described for as described above for the secondary efficacy analysis for IGA. In addition, a logistic regression analysis similar to that described above, will also be performed for this ITT population for all observed cases.

Another supplementary analysis will be performed using the ITT population in which data from assessments performed after rescue therapies are received are excluded and a last observation carried forward approach applied for missing data. The logistic regression and MCP-Mod dose response model used for this analysis and the presentation of results will be similar as described above for the secondary efficacy analysis for IGA. In addition, a logistic regression analysis like that described above, will also be performed for this ITT population with LOCF.

Another supplementary analysis will be performed using the ITT population excluding data from subjects CCI whose treatment allocations were accidentally unblinded at the site. The analysis will be performed using the same MCP-Mod as described above for the secondary efficacy analysis for IGA.

Furthermore, an analysis will be performed using a generalized estimating equation (GEE) model for repeated measures including treatment group, randomization stratum (total serum IgE < 150 kU/L or \geq 150 kU/L), baseline IGA value, visit, and visit by treatment group interaction as covariates. The analysis will be conducted including data from visits up to Week 24. The model will use a logistic link function and an independence working correlation matrix. If the assumed working correlation matrix will not fit, then suitable alternatives including exchangeable, unstructured, and autoregressive matrixes will be explored. From the model obtained, estimates of the treatment effect at each visit together with the associated standard errors, 90% CIs, and p-values will be provided.

Percentage of Subjects Achieving EASI 50, EASI 75, or EASI 90 at Week 16

The percentage of subjects achieving EASI 50, EASI 75, or EASI 90 at Week 16 will be analyzed separately a logistic regression model including treatment group and randomization stratum (total serum IgE level < 150 kU/L or \geq 150 kU/L) as categorical factors, and baseline EASI score as a covariate for each endpoint. The composite estimand will be the difference between MEDI3506 and placebo in EASI 50, EASI 75, or EASI 90 response rate at Week 16 in the ITT population. Subjects who discontinue investigational product, withdraw from the study, or require rescue therapy will be considered as non-responders. For each MEDI3506 group compared with placebo, differences in response rates, 90% CIs for the differences in response rates (Ge et al, 2011), and two-sided p-values will be reported for each endpoint. If the number of responders is < 5 in any MEDI3506 group, the logistic regression model will not be used. Instead, the 90% CI and p-value for the difference in response rates will be calculated using an unconditional exact method (Chan and Zhang, 1999).

As a supportive analysis for EASI 75, the percentage of subjects achieving an EASI 75 response at Week 16 will be analyzed for the ITT population using an MCP-Mod dose response model similar to that described above for IGA response. Results obtained from the analysis will also be described in a similar way as described for the IGA response.

Barplot of the percentage of subjects achieving EASI 50, EASI 75, or EASI 90 at Week 16 will be provided. A plot showing the percentage of subjects achieving an EASI 50 response

in each treatment group by visit will also be provided. Similar plot will be provided for EASI 75 and EASI 90.

Change from Baseline to Week 16 in % BSA Affected by AD

The endpoint of change from baseline in % BSA affected by AD, as assessed by EASI, will be summarized descriptively and analyzed for the ITT population using a MMRM. Data from visits after subjects receive rescue therapy will be excluded from the analysis. Details of the model are similar to those described for percent change from baseline to Week 16 in EASI score (Section 3.4.1.3).

A plot of the adjusted mean change from baseline (\pm standard error) in %BSA by visit will be provided.

Peak Pruritus NRS at Week 16

The endpoint change from baseline to Week 16 in weekly mean of daily peak pruritus NRS will be summarized descriptively and analyzed using a MMRM. Data from visits after subjects receive rescue therapy will be excluded from the analysis. Details of the model are similar to those described for percent change from baseline to Week 16 in EASI score (Section 3.4.1.3)

The endpoint percentage of subjects achieving a ≥ 3 point reduction from baseline to Week 16 in weekly mean of daily peak pruritus NRS will be analyzed using a logistic regression model including treatment group and randomization stratum (total serum IgE < 150 kU/L or ≥ 150 kU/L), and baseline weekly mean of daily peak pruritus score as a covariate. Other details of the model are similar to those described above for the analyses of the secondary efficacy endpoint of EASI 50.

Skin pain NRS at Week 16

Change from baseline to Week 16 in weekly mean peak skin pain NRS will be summarized descriptively and analyzed using a MMRM. Data from visits after subjects receive rescue therapy will be excluded from the analysis. Details of the model are similar to those described for percent change from baseline to Week 16 in EASI score (Section 3.4.1.3).

Percent Change from Baseline to Week 16 in SCORAD

The endpoint of percent change from baseline to Week 16 in SCORAD will be analyzed using a MMRM, including data from visits up to Week 16. Data from visits after subjects receive

rescue therapy will be excluded from the analysis. Details of the model are similar to those described for percent change from baseline to Week 16 in EASI score (Section 3.4.1.3).

A cumulative distribution plot of percent change from baseline in SCORAD will be presented. In addition, descriptive summary of the total SCORAD score at each visit will be provided by treatment group. In addition, similar summary will be provided for each of the components of SCORAD (extent, intensity, pruritus, sleep loss, objective). In addition, summary of change from baseline will be provided by visit for the total SCORAD score and separately for each of the components.

PGI-S at Week 16

The PGI-S will be summarized with descriptive statistics including number of subjects, mean, SD, median, minimum, and maximum at each visit. In addition, the number and percentage of subjects in each category will be summarized by visit.

Change from Baseline to Week 16 in 5-D Itch

The endpoint change from baseline to Week 16 in 5-D itch will be summarized descriptively and analyzed using a MMRM, including data up to Week 16. Data from visits after subjects receive rescue therapy will be excluded from the analysis. Details of the model are similar to those described for percent change from baseline to Week 16 in EASI score (Section 3.4.1.3).

In addition, descriptive summary of the total 5-D itch score at each visit will be provided by treatment group. Similar summary will be provided for each of the domains of 5-D itch (duration, degree, direction, disability, distribution). In addition, summary of change from baseline will be provided by visit for the total 5-D itch score and separately for each of the domains.

Change from Baseline to Week 16 in POEM

The endpoint change from baseline to Week 16 in POEM will be summarized descriptively and analyzed using a MMRM, including data up to Week 16. Data from visits after subjects receive rescue therapy will be excluded from the analysis. Details of the model are similar to those described for percent change from baseline to Week 16 in EASI score (Section 3.4.1.3).

Change from Baseline to Week 16 in DLQI

The endpoint change from baseline to Week 16 in DLQI will be summarized descriptively and analyzed using a MMRM, including data up to Week 16. Data from visits after subjects

receive rescue therapy will be excluded from the analysis. Details of the model are similar to those described for percent change from baseline to Week 16 in EASI score (Section 3.4.1.3).

In addition, descriptive summary of the total DLQI score at each visit will be provided by treatment group. Similar summary will be provided for each of the components of DLQI (daily activities, leisure, personal relationship, work or school, symptoms and feelings, treatment side effects). In addition, summary of change from baseline will be provided by visit for the total DLQI score and separately for each of the components.

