2.2 Secondary Objectives and Associated Endpoints

Table 2 Secondary Objectives and Associated Endpoints

Type	Objective	Endpoint
Efficacy		EASI: Percentage of subjects achieving a 90% reduction from baseline in EASI score (EASI 90) at Week 16.
		 Percentage of subjects achieving a 75% reduction from baseline in EASI score (EASI 75) at Week 16.
	To further assess the effects of MEDI3506 compared with placebo on AD disease severity and symptoms, in adult subjects with moderate-to-severe AD.	 Percentage of subjects achieving a 50% reduction from baseline in EASI score (EASI 50) at Week 16.
		Percentage of subjects achieving an IGA of 0 (clear) or 1 (almost clear) with at least a 2 grade reduction from baseline score at Week 16.
		 Peak pruritus NRS: Percentage of subjects achieving a reduction of ≥ 3 from baseline to Week 16 in weekly mean of daily peak pruritus NRS.
		Peak pruritus NRS: Change from baseline to Week 16 in weekly mean of daily peak pruritus NRS.

Table 2 Secondary Objectives and Associated Endpoints

Type	Objective	Endpoint
		 Skin pain NRS: Change from baseline to Week 16 in weekly mean of daily peak skin pain NRS. SCORAD: Percent change from baseline to Week 16. PGI-S at Week 16. Change from baseline to Week 16 in: % BSA affected by AD. 5-D itch. POEM. DLQI.
Safety	To assess the safety and tolerability of MEDI3506 compared with placebo, in adult subjects with moderate-to-severe AD.	During the treatment and follow-up periods: TEAEs and TESAEs. Vital signs. Safety laboratory analysis. ECGs. The following parameters will be recorded for each ECG: Date and time of ECG. Heart rate (beats/min). QT (ms). Overall evaluation (normal/abnormal). Left ventricular ejection fraction as measured by echocardiogram.
PK	To evaluate the PK of MEDI3506 in adult subjects with moderate-to-severe AD.	Serum MEDI3506 concentration profiles during the treatment and follow-up periods.
Immunogenicity	To evaluate the immunogenicity of MEDI3506 in adult subjects with moderate-to-severe AD.	Incidence of ADA during the treatment and follow-up periods.

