2.4 Sample Size

A sample size of 144 subjects in an overall 3:1:1:3 ratio of MEDI3506 CCI : MEDI3506 CCI : MEDI3506 CCI : pooled placebo will provide at least 90% power to detect a statistically significant difference in the percent change from baseline to Week 16 in EASI score between the highest dose of MEDI3506 and pooled placebo in a responder subgroup, assuming a 35% point difference between placebo and MEDI3506 at the highest dose, based on a SD of 40% points, a two-sided 10% alpha level and 50% of subjects in the responder subgroup. Based on identical assumptions, the sample size provides > 99% power to detect a statistically significant dose response in percent change from baseline to Week 16 in EASI score in all-comers.

The calculations for dose-response assume that percent change from baseline to Week 16 in EASI score will increase monotonically with the administration of higher MEDI3506 doses. The power was calculated using a multiple comparison procedure with modelling techniques (MCP-Mod) (Bretz et al, 2005) with 4 candidate models for the dose response (linear, maximum effect attributable to the drug [E_{max}], and 2 Hill- E_{max} models). Randomization will be stratified by total IgE (< 150 kU/L or \geq 150 kU/L) at screening. The sample size calculations were performed using the R statistical computing software.

To allow for the possibility that \leq 5% of the subjects per treatment group (for MEDI3506 CCI and placebo) may be ineligible for the ITT population, the total sample size will comprise approximately 152 subjects (58 MEDI3506 CCI, 18 for MEDI3506 CCI, 18 for MEDI3506 CCI, and 58 for pooled placebo) randomized approximately to 3:1:1:3 ratio overall to the treatment groups.

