3 STATISTICAL METHODS

3.1 General Considerations

In general, unless specified otherwise, baseline is defined as the last non-missing assessment prior to dosing. If the baseline is missing following the above definition, baseline evaluations will not be imputed and will be considered as missing. All safety analyses will be performed on the As-treated population. All PK analyses will be conducted using the PK-population. Immunogenicity evaluation will be based on the As-treated population. All other analyses will be performed on the ITT population unless stated otherwise. All data will be provided in data listings sorted by treatment group and subject number. The placebo CCI groups will be pooled for planned analyses, except where stated otherwise. All tabular summaries will be presented by treatment group. Categorical data will be summarized by the number and percentage of subjects in each category. Continuous variables will be summarized by descriptive statistics including number of subjects, mean, standard deviation (SD), median, minimum, and maximum. All statistical tests will be two-sided at an alpha = 0.1 significance level unless stated otherwise.

Day 1 is the first dosing date. Prior to Day 1, study days will be calculated as (sample collection date – Day 1). After Day 1, study days will be calculated as (sample collection date – Day 1 + 1).

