3.4.2 Secondary Efficacy Endpoints and Analyses

3.4.2.1 Secondary Efficacy Endpoints

Secondary efficacy endpoints will be measured up to Week 16 for on-therapy effects and at time points beyond the end of treatment for off-therapy effects.

IGA

The IGA consists of a 5-point severity scale from clear to severe disease (0 = clear, 1 = almost clear, 2 = mild disease, 3 = moderate disease, and 4 = severe disease). The secondary efficacy IGA endpoint is the percentage of subjects achieving both an IGA score of 0 (clear) or 1 (almost clear) and a reduction from baseline of ≥ 2 points at Week 16.

EASI including Percentage BSA Affected by AD

Secondary efficacy endpoints based on EASI include, as follows:

- Percentage of subjects achieving a 90% reduction from baseline in EASI score (EASI 90) at Week 16
- Percentage of subjects achieving a 75% reduction from baseline in EASI score (EASI 75) at Week 16
- Percentage of subjects achieving a 50% reduction from baseline in EASI score (EASI 50) at Week 16
- Change from baseline to Week 16 in the percentage of BSA affected by AD, as assessed by EASI.

Pruritus NRS

Pruritus will be assessed using an NRS (0 to 10) with 0 = no itch and 10 = worst imaginable itch. Daily peak pruritus NRS assessments will be summarized as weekly means. The weekly mean score will be set to missing if > 3 assessments are missed in that 7-day period. Baseline will be defined as an average of the last 7 days prior to study drug being administered. If more than 3 days have missing data in the baseline period, the baseline period will be shifted back to the last 7-day period which includes at least 4 non-missing days.

The secondary efficacy endpoints based on pruritus NRS include:

- Change from baseline to Week 16 in weekly mean of daily peak pruritus NRS, and
- Percentage of subjects achieving a reduction of ≥ 3 from baseline to Week 16 in weekly mean of daily peak pruritus NRS.

Skin Pain NRS

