Appendix 1 Determination of dose-response profile using MCP-Mod

To determine dose-response profile using MCP-Mod, the candidate models first need to be defined. For this study, four candidate models will be used for the MCP-Mod models and these are: Linear, E_{max} and 2 Hill- E_{max} models. The description of the function of each model and the parameters are specified below:

- Linear Model: $f(d, \theta) = E_0 + \delta d$
- E_{max} Model: $f(d, \theta) = E_0 + E_{max} \frac{d}{ED_{50} + d}$
- Hill- E_{max} Model: $f(d, \theta) = E_0 + E_{max} \frac{d^h}{ED_{50}^h + d^h}$

where d denotes the dose parameter; E_0 is the placebo effect; δ is the slope parameter for the linear model; E_{max} is the asymptotic maximum effect; ED_{50} is the dose giving half of the asymptotic maximum effect; h is the hill parameter which determines the steepness of the model as the ED_{50} .

For the percent change from baseline to Week 16 in EASI endpoint, the models are defined as follows:

$$fmodels = Mods(linear = NULL, emax = 150, sigEmax = rbind(c(150,3), c(450,3)), \\ doses = c(\text{CCI}), placEff=0, maxEff=35, direction = c("decreasing")).$$

where $maxEff$ is the maximum effect over placebo.

For the percentage of subjects achieving IGA response at Week 16 endpoint, the models are defined as follows on the logit scale:

$$fmodels = Mods(linear = NULL, emax = 150, sigEmax = rbind(c(150,3), c(450,3)), \\ doses = c(\text{CCI}), placEff=logit(10), maxEff=logit(30)-logit(10), \\ direction=c("increasing"))$$

where $logit(x)$ is $\log(x/(1-x))$.

For the percentage of subjects achieving EASI 75 response at Week 16 endpoint, the models are defined as follows:

$$fmodels = Mods(linear = NULL, emax = 150, sigEmax = rbind(c(150,3), c(450,3)), \\ doses = c(\text{CCI}), placEff=logit(15), maxEff=logit(35)-logit(15), \\ direction=c("increasing")).$$

Once the models are defined, then the MCP-Mod analysis is performed. For the percent change from baseline to Week 16 in EASI endpoint, the MCP-Mod analysis is performed as follows:

$$MM = MCPMod(dose = doses, EstEffects, S = vCov, models = fmodels, type = "general", placAdj = FALSE, Delta = 35, alpha = 0.1, alternative = c("two.sided"))$$

where

- “*doses*” denotes the vector of doses,
- “*EstEffects*” denotes the vector of estimated coefficient obtained from the MMRM,
- “*vCov*” denotes the estimated variance-covariance matrix,
- “*fmodels*” is the specified candidate models,

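### PGI-S at Week 16 is a secondary endpoint under a versus-placebo objective, but the SAP gives it no treatment comparison

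*SAP*

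**What the plan says.** Protocol 2.2 (Table 2) places PGI-S at Week 16 among the secondary efficacy endpoints, all under one objective: "To further assess the effects of MEDI3506 compared with placebo on AD disease severity and symptoms". Protocol 4.3.1.9 and SAP 3.4.2.1 both give PGI-S six ordered responses, from no symptoms to very severe.

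The analysis text in SAP 3.4.2.3 reads: "The PGI-S will be summarized with descriptive statistics including number of subjects, mean, SD, median, minimum, and maximum at each visit". It adds the number and percentage of subjects in each category by visit. By contrast, the IGA endpoint in the same section, "The percentage of subjects achieving an IGA score of 0 (clear) or 1 (almost clear) and a reduction from baseline of ≥ 2 points", is modelled against placebo. SAP 3.4.3.10 repeats the PGI-S summaries for the other weeks, and Protocol 4.8.3.3 has the same descriptive plan. SAP 3.1 sets the general rule for inference: "All statistical tests will be two-sided at an alpha = 0.1 significance level unless stated otherwise". No test is attached to PGI-S.

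The SAP version history records that version 3 removed a repeated-measures model for PGI-S. The reason given is that the analysis was not needed because the scale is not really continuous.

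**The concern.** An objective framed as a comparison with placebo needs at least one estimate of that comparison for each endpoint listed under it. For PGI-S, a reader of the study report would see category percentages by arm and have to judge the difference by eye, with no measure of its precision.

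The recorded reason for dropping the model does not lead to having no comparison. A scale that is ordered but not continuous calls for an ordinal method. The remaining text also reports means and SDs of the category codes, which treats the scale as continuous after all.

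**Working it through.** **Endpoints side by side.** Protocol Table 2 has thirteen secondary efficacy endpoints. SAP 3.4.2.3 treats them as follows.

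- IGA 0/1 response: logistic regression and MCP-Mod.
- EASI 50, EASI 75, EASI 90 and the pruritus NRS reduction of at least 3: logistic regression, or an exact method when responders are few.
- Change in pruritus NRS, skin pain NRS, % BSA, 5-D itch, POEM and DLQI, and percent change in SCORAD: MMRM on the pattern of the primary analysis, which gives differences from placebo with 90% CI and p-value.
- PGI-S: descriptive statistics and category percentages only.

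Twelve of the thirteen have a between-arm estimate; PGI-S is the exception. SAP 3.4.2.2 sets rescue handling for the responder endpoints and for the continuous endpoints. PGI-S appears in neither list.

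**Are the data there?** Protocol Table 7 schedules PGI-S at Visit 3 (baseline) and Visit 10 (Week 16). A Week 16 model with baseline as covariate needs nothing new.

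**The plan's own power figure.** Only EASI is powered. SAP 2.4 has "A sample size of 144 subjects in an overall 3:1:1:3 ratio", so the top dose and pooled placebo have 144 × 3/8 = 54 each, the lower doses have 144 × 1/8 = 18 each, and half of 54 is 27 for the responder subgroup. With a difference of 35, SD 40 and two-sided 10%: 35 / (40 × √(2/27)) = 3.215, and Φ(3.215 − 1.645) = 94%. This meets the stated figure of at least 90%. No power is stated for PGI-S, so nothing there can be reproduced.

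**What an ordinal comparison could detect (for scale only).** For a proportional-odds comparison of n1 v n2 subjects, the information on the log odds ratio is about V = n1·n2 / (3(n1+n2)) × (1 − S). S is the sum of the cubed category proportions averaged over the two arms. Power is Φ(ln(OR)·√V − 1.645). The documents give no PGI-S distribution, so S is assumed. Six equal categories give S = 6 × (1/6)³ = 0.028; S = 0.06 stands for a distribution bunched in the moderate and severe levels; S = 0.10 is a more bunched case.

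54 v 54, S = 0.06: V = 54 × 54 / 324 × 0.94 = 8.46, √V = 2.909.

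- OR 2: 0.693 × 2.909 − 1.645 = 0.371, power 64%.
- OR 2.5: 0.916 × 2.909 − 1.645 = 1.020, power 85% (simulation gives about 84%).
- OR 3: 1.099 × 2.909 − 1.645 = 1.551, power 94%.

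For S from 0.028 to 0.10 the ranges are 63–66%, 83–86% and 93–95%.

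18 v 54, S = 0.06: V = 18 × 54 / 216 × 0.94 = 4.23, √V = 2.057, so power is about 41%, 60% and 73%. A lower-dose arm would give an estimate with a wide interval. All three odds ratios are assumptions.

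**PGI-S definition.** Protocol 4.8.3.3 describes a 3-point scale (mild, moderate, severe). Protocol 4.3.1.9 and SAP 3.4.2.1 have six levels. The question wording in SAP 3.4.2.1 also differs from that in Protocol 4.3.1.9.

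**The case against.** The descriptive plan looks deliberate. Protocol and SAP agree on it, and the version history says the model was judged unnecessary as well as unsuitable. PGI-S is reported on its own scale through the category percentages. The objective covers many endpoints, and five other patient-reported measures (pruritus NRS, skin pain NRS, 5-D itch, POEM, DLQI) are compared with placebo, so patient-reported benefit does not go untested. These facts stand and keep the point minor. They do not explain why one endpoint under a comparative objective has no comparison.

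A second objection is that proportional odds may fail. Placing rescued and withdrawn subjects in the worst category can strain it: if those events are equally frequent in both arms, one odds ratio cannot hold at every cut. This also stands. It is a reason to call the model supportive and to keep the category percentages beside it, where a reader can see whether one odds ratio is a fair summary.

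**Conclusion.** The gap is real and small. PGI-S is the only secondary efficacy endpoint without a between-arm estimate, CI or test, and this follows from the text without any assumption. The power figures of about 64%, 84% and 94% at 54 v 54 rest on assumed odds ratios, an assumed category distribution and proportional odds. They show only that the comparison would be informative for a moderate to large effect at the top dose.

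A reader might infer that IGA has the same fault, and that its key secondary analysis loses about 12 points of power by using the 0/1 cut of a five-level scale. The documents do not support that. Protocol 2.2 and SAP 3.4.2.1 define the IGA endpoint as a percentage of responders, and SAP 3.4.2.3 defines its estimand as a difference in response rates, so the analysis matches both. An ordinal IGA model would answer a different question and leave the power of the key secondary unchanged.

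The apparent gain also depends on an odds ratio of (0.30/0.70)/(0.10/0.90) = 3.86 holding at every cut. The 10% and 30% are the candidate-model inputs in SAP Appendix 1, not an ordinal assumption. If it does hold, power at 54 v 54 is 84% binary against 95–99% ordinal. With the same 10% to 30% change, ordinal power is 76% if the log odds ratio is halved at the cuts between grades 2, 3 and 4. It is about 59% if the extra responders come proportionally from grades 2 to 4, and 18% if they come only from grade 2. The sign of the difference is therefore not established.

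**What to change.** In SAP 3.4.2.3, keep the PGI-S category percentages and add one supportive analysis before unblinding: a proportional-odds model of the Week 16 PGI-S category with treatment group, IgE stratum and baseline PGI-S. Place subjects who received rescue therapy or withdrew from the study in the worst category, in line with the IGA composite estimand, and state how a Week 16 value missing for any other reason is handled. Report the odds ratio with 90% CI for each dose against pooled placebo. Add PGI-S to the handling rules in SAP 3.4.2.2.

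Reconcile the 3-point description in Protocol 4.8.3.3 with the six levels in Protocol 4.3.1.9 and SAP 3.4.2.1, and align the question wording.

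The cost is a paragraph of SAP text and one model on data already collected. The downsides are a proportional-odds assumption and one more supportive result to interpret. The IGA analyses stay as they are.
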